If GVHD signs/symptoms worsen during the taper of itacitinib/placebo (ie, first flare), the dose may be escalated by 1 dose level. If the participant requires addition or initiation of a new systemic therapy or experiences subsequent flare, then the participant would be considered as having progression of disease and would be withdrawn from study treatment. A short pulse of corticosteroids may be used once, without being considered progression, as long as the dose does not exceed the corticosteroid dose on Day 1 and can be tapered to physiological doses of 6 to 8 mg/day of methylprednisolone (or 7.5-10 mg/day of prednisone) within 6 weeks from starting.

After completion of an itacitinib/placebo taper, if reappearance or worsening of cGVHD occurs, the participant may be treated per institutional practice.

Participants who do not achieve or maintain a CR or PR at Day 180 who are still receiving benefit from itacitinib/placebo per investigator clinical judgment may continue on study treatment for a maximum total treatment duration of 36 months.

If the participant is not receiving benefit from itacitinib/placebo per investigator judgment, the participant must discontinue study treatment and be treated per institutional practice. However, if mixed response or stable/unchanged disease is assessed, it is recommended that a new systemic therapy be initiated after confirmation at the next scheduled visit, at least 4 weeks later. These participants will be followed for survival.

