6.1.2.4. Management of Corticosteroids During cGVHD Flare

If cGVHD flares during a corticosteroid taper, the dose of corticosteroids may be re-escalated at the investigator's discretion and will not be considered treatment failure. If the flare requires addition or initiation of new systemic therapy or re-escalation of prednisone or methylprednisolone at a dose exceeding the dose on Day 1, the participant will be considered to have experienced treatment failure and must be withdrawn from study treatment. The use of

systemic corticosteroids other than prednisone or methylprednisolone will not be considered initiation of new systemic therapy as long as the dose does is not higher than the equivalent prednisone dose on Day 1. This guidance applies to all randomized participants.

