7.1. General Considerations

In Part 1, all efficacy analyses will be performed using the safety run-in population. In Part 1 Expansion, all efficacy analyses will be performed using the safety population.

If there are not sufficient data for meaningful statistical inference, the planned analysis will not be performed, and only related summary statistics and/or listings will be provided.

In all efficacy analyses, initiation of new systemic anti-GVHD therapy includes 4 scenarios:

1. Initiation of new anti-GVHD therapy including a higher dose of corticosteroid than that used at Day 1.
2. The need for a second dose increase in corticosteroids.
3. A dose increase in corticosteroids that is not tapered back to the previous dose of corticosteroids within 6 weeks (\pm 2 days) of the increase.
4. Reintroduction of systemic corticosteroids that occurs after complete taper of corticosteroids due to response.

No formal statistical tests will be performed.

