11.1. Changes to Protocol-Defined Analyses

Note that the ITT population is equivalent to the safety analysis set as defined in the Protocol.

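### SAP 7.1 counts a second steroid increase, or one not reversed within 6 weeks, as new systemic therapy at any dose; Protocol 6.1.2.4 does not up to the Day 1 dose, and the SAP does not declare the difference

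*SAP*

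**What the plan says.** SAP 7.1 applies its rule to every efficacy endpoint and names four events that count as new systemic anti-GVHD therapy:

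- Scenario 1, on which the two documents agree, turns on the Day 1 dose: a steroid dose above it, or other new treatment, counts.
- Scenario 2 sets no dose threshold at all. It reads "The need for a second dose increase in corticosteroids".
- Scenario 3 adds a time limit, with a 2-day allowance, again without a dose threshold. It reads "A dose increase in corticosteroids that is not tapered back to the previous dose of corticosteroids within 6 weeks".
- Scenario 4 concerns participants who had already stopped steroids because they responded and then restart them.

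Under SAP 7.3.1, new systemic therapy at or before the Month 3, 6 or 12 assessment makes the participant a nonresponder. Under SAP 7.3.3 it ends duration of response.

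Protocol 6.1.2.4 covers flares while steroids are being tapered: "If cGVHD flares during a corticosteroid taper, the dose of corticosteroids may be re-escalated". It leaves this to the investigator and says that it is not treatment failure. Failure arises only if the dose goes above the Day 1 dose or another new systemic therapy is needed. Protocol 4.1.2 defines treatment failure as cGVHD progression, death or the start of new systemic cGVHD therapy.

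Protocol 6.1.1.6 deals with worsening during the taper of itacitinib or placebo: "A short pulse of corticosteroids may be used once, without being considered progression". The pulse must not exceed the Day 1 dose and must reach a physiological dose within 6 weeks.

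SAP 11.1, the place for departures from the protocol, has one line: "Note that the ITT population is equivalent to the safety analysis set as defined in the Protocol". SAP 11.2 says Section 7 was updated to align with Protocol Amendment 8.

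**The concern.** Responder status is meant to be a property of the participant and the endpoint definition. Here it also depends on which document the programmer follows. A participant who flares twice during the steroid taper, is re-escalated each time to no more than the Day 1 dose, and is in PR at Day 180 is a responder on the protocol's definition (CR or PR at the timepoint) and a nonresponder under the SAP. Duration of response differs in the same way.

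Month 3 and Month 6 response are the key secondary endpoints of Part 1 expansion. They are summarised to support the Part 2 dose decision (Protocol 6.1.1.4), and the Month 6 posterior probability may be used by the DMC (Protocol 10.1.2). Part 1 expansion is open-label and re-escalation is discretionary, so a rule that turns steroid changes into nonresponse also makes the endpoint depend on decisions taken with treatment known.

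**Working it through.** **Step 1: compare the rules, scenario by scenario.**

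| SAP 7.1 scenario | Flare during steroid taper (Protocol 6.1.2.4) | During itacitinib/placebo taper (Protocol 6.1.1.6) |
|---|---|---|
| 1. Dose above Day 1 | Agrees: treatment failure | Agrees: a pulse above the Day 1 dose is not exempt |
| 2. Second increase | Conflicts at or below the Day 1 dose: no limit on number | Partly agrees: pulse once only; a subsequent flare is progression |
| 3. Not back to the previous dose in 6 weeks | Conflicts at or below the Day 1 dose: no limit on duration | Partly agrees: 6-week limit, but the target is a physiological dose, not the previous dose |
| 4. Reintroduction after complete taper due to response | Not covered: this section concerns flares while the taper is under way | Conflicts with the one-time pulse if steroids had been fully tapered |

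The conflict in scenarios 2 and 3 follows from the protocol's own definition. New systemic cGVHD therapy is one component of treatment failure, so an event declared not to be treatment failure cannot be new systemic cGVHD therapy. The documents also agree that a single increase at or below the Day 1 dose, returned to the previous dose within 6 weeks, is not an event.

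**Step 2: which timepoints are reached.** Steroid taper starts by Day 14, and weekly 10% cuts run from Day 56 (Protocol Table 17). If each cut is 10% of the Day 56 dose (an assumption), the taper ends at 56 + 10 × 7 = Day 126. Flares during that taper, and so scenarios 2 and 3, can fall before Day 90 and Day 180. For scenario 3, even if the event is dated at the end of the 6 weeks, an increase by Day 90 − 42 = 48 counts at Month 3 and one by Day 180 − 42 = 138 counts at Month 6, give or take the 2 days.

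The itacitinib/placebo taper starts on or after Day 365, or between Day 180 and Day 365 in sustained CR. The clash between the pulse and scenario 4 therefore bears on Month 12 response and duration of response. A restart of steroids after complete taper but before the itacitinib taper has no explicit protocol rule.

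**Step 3: size.** Protocol Table 23 (SAP Table 3) gives the posterior probability of a clinically meaningful difference:

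P(p_I − p_C > d), with p_I ~ Beta(a + s_I, b + 35 − s_I) and p_C ~ Beta(a + s_C, b + 35 − s_C).

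The prior and d are not visible in the public text. With a = b = 1 and d = 0.15, all 30 cells reproduce to within 0.05 points. Both values are inferred from that fit, and the results below are read directly from the table.

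The number reclassified is not given in the documents, so 1 or 2 per arm is an assumption. Each moves an arm's response rate by 1/35 = 2.9 points.

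| Reclassified as nonresponders | Itacitinib v control | Posterior |
|---|---|---|
| None | 28 v 20 | 73.9% |
| 1 itacitinib | 27 v 20 | 64.7% |
| 2 itacitinib | 26 v 20 | 54.9% |
| 1 control | 28 v 19 | 81.3% |
| 2 control | 28 v 18 | 87.2% |
| 1 in each arm | 27 v 19 | 73.4% |
| 2 in each arm | 26 v 18 | 73.1% |

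Two reclassifications move the posterior by −19.0 points (54.9 − 73.9) or +13.3 points (87.2 − 73.9), depending on the arm. Two in each arm move it by −0.8 points (73.1 − 73.9).

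**The case against.** The best defence is that Protocol 6.1.2.4 governs withdrawal from study treatment, while SAP 7.1 defines an endpoint. Protocol 10.4 calls itself a summary and leaves analysis detail to the SAP. A responder rule stricter than the treatment-stopping rule is legitimate. That much stands. It does not answer the lack of disclosure: the SAP uses the protocol's own term, new systemic therapy, gives it a wider meaning, omits this from its list of changes, and describes Section 7 as aligned with the protocol.

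Three further objections narrow the point and are accepted:

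- During the itacitinib/placebo taper, Protocol 6.1.1.6 partly matches scenarios 2 and 3.
- Scenario 4 has no shown conflict at Month 3 or Month 6.
- Dose selection rests primarily on adverse events, with response in support (SAP 7.2), and no formal tests are planned.

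A reader might also infer that the SAP rule penalises the arm with the most complete tapers, because scenario 4 requires one. The documents do not support this. Scenario 4 also requires a restart, so flare rates matter as well. Scenarios 2 and 3 could be commoner on steroids alone, which would favour itacitinib. No rates are given.

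**Conclusion.** The contradiction is established from the text for scenarios 2 and 3 at doses up to the Day 1 dose, for flares during the steroid taper. It can change Month 3 and Month 6 response and duration of response. The scenario 4 conflict is narrower: it is confined to the one-time pulse during itacitinib/placebo taper, and so to Month 12 response and duration of response.

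The size cannot be fixed in advance. Under the assumed two reclassifications from 28 v 20, the posterior lies anywhere from 54.9% to 87.2%, and with two in each arm it barely moves. It would be tempting to quote only the fall that follows from removing itacitinib responders, but the SAP rule applies to every arm and nothing in the documents makes that case the likely one. The finding is that classification is ambiguous and undeclared, not that there is a bias in a known direction.

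**What to change.** Reconcile SAP 7.1 with Protocol 6.1.2.4 and 6.1.1.6 so that one rule defines new systemic therapy. The rule should cover number of increases, duration, the 6-week target dose, and reintroduction after complete taper. It should also fit SAP 6.4, which handles a short pulse after a completed taper only as a break in treatment duration. If the SAP is meant to stay stricter than the protocol, list that in SAP 11.1 with the reason. In either case, tabulate Month 3, 6 and 12 response and duration of response under both the protocol rule and the SAP rule. Where the protocol is silent, state the convention used. Which clinical rule is right is for the sponsor to decide.

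The cost is SAP wording and one extra set of tables. Steroid changes made to manage flares are already reported on the eCRF (Protocol 8.2.2), so no new data are needed.

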7.2. Primary Analysis

In Part 1, the primary objective is to identify an appropriate dose of itacitinib (200 mg QD or 300 mg QD) in combination with corticosteroids as initial treatment for moderate or severe cGVHD. The DLT data through Day 28 and additional data from clinical safety and laboratory assessments will be used as primary endpoints for this analysis.

In Part 1 Expansion, the primary objective is to identify an appropriate dose of itacitinib (300 mg QD, 400 mg QD, or 300 mg BID) in combination with corticosteroids as initial treatment for moderate or severe cGVHD. The selection of the dose is primarily based on the incidence and severity of AEs across treatment cohorts and will be supported by cGVHD response data (refer to Section 10.1.2 of the Protocol).

7.3. Analyses of the Secondary Efficacy Parameters

7.3.1. Response Rate

Response rate at 3, 6, and 12 months (Days 90, 180, and 365) is defined as the proportion of participants who achieved a response (CR or PR) at each of these timepoints based on an ITT population.

A participant will not be considered a responder for the analysis of ORR at 3, 6, and 12 months if any of the following events occurred at or prior to the response assessment at the predefined timepoint:

- cGVHD progression per NIH response criteria or initiation of a new systemic therapy for cGVHD

- Evidence of progression of the underlying hematologic disease
- Withdrawal from the study
- Death
- Response assessment missing (not performed) at the predefined timepoint

The proportion of responders will be estimated with 95% CIs. Confidence intervals will be calculated based on the exact method for binomial distributions. Summary statistics will be provided.

Additional analyses may be performed based on evaluable subsets. An evaluable population will also be considered with participants who have completed 3, 6, or 12 months of follow-up as of the cutoff date or discontinued earlier because of new cGVHD progression. Presentations of ORR at Month 3 and Month 6 will include a footnote explaining what "evaluable" means (ie, participants who had at least 3 or 6 months of follow-up as of the cutoff date or discontinued earlier).

Summary statistics and 95% CI will be provided by cohort. The primary comparisons in Part 1 expansion will involve only the 2 itacitinib groups (Treatment Groups A and B) and the corticosteroids-only group (Treatment Group D) as a result of Protocol Amendment 8, in which Treatment Group C (300 mg BID + corticosteroids) was discontinued. Data from Treatment Group C will be presented only as summary statistics and will not be subjected to any statistical comparison.

Pairwise Cochran-Mantel-Haenszel tests will be conducted for Month 6 response rate for each of the 2 itacitinib groups (Treatment Groups A and B) and the corticosteroids-only group (Treatment Group D) as an exploratory analysis.

The secondary endpoints discussed below will be summarized by Treatment Groups A, B, and D using the ITT population for efficacy-related endpoints and all groups for safety-related endpoints.

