2.3.2.3. Preliminary Results for Part 1 Expansion

Preliminary data from the Part 1 expansion was reviewed ad hoc by an independent DMC. At the data cutoff date for the ad hoc DMC review (09 JUL 2021), 107 participants had been enrolled in the Part 1 expansion portion of the study in the 300 mg QD dose cohort (Treatment Group A; n = 32), 400 mg QD dose cohort (Treatment Group B; n = 25), 300 mg BID dose cohort (Treatment Group C; n = 24), and corticosteroid monotherapy dose cohort (Treatment Group D; n = 26). The median duration of exposure was 83 days (range: 2-579 days) across the itacitinib treatment groups. At the time of the data cutoff, 62 participants remained on treatment across the 4 treatment groups.

Malignancy relapse was the most frequent reason for discontinuation in Treatment Group C (itacitinib 300 mg BID in combination with corticosteroids). Although no interim analysis was planned, and the number of participants was small, with 4 confirmed relapses reported in this cohort versus 1 relapse in each of the 300 mg QD and 400 mg QD cohorts and no relapse in the corticosteroids alone cohort, the sponsor had decided, following the DMC recommendation, to discontinue the itacitinib 300 mg BID study arm.

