2.4. Benefit/Risk Assessment

The potential benefit for itacitinib in moderate to severe cGVHD patients is based on available preclinical data demonstrating inhibition of the JAK/STAT pathway implicated in the previously described pathogenesis of cGVHD.

Risks to study participants may be minimized by compliance with the eligibility criteria and study procedures as well as close clinical monitoring and adherence to dose modification guidelines for toxicity. Risks related to myelosuppression and bleeding should be further managed in accordance to standard institutional practices for administration of hematopoietic growth factors and transfusion support. Risks related to infections should be managed through continued prophylaxis and prompt identification and treatment.

Progressive multifocal leukoencephalopathy (PML) is a rare complication in allo-HCT recipients. Actions to minimize the risk of PML in cGVHD participants will follow standard allo-HCT guidelines, including close monitoring of any clinical signs of progressive focal

neurological symptoms, with prompt diagnostic work-up and treatment. Any case of PML should be reported as per the process described in Section 9.4.

Recent animal studies of itacitinib in rats showed development of benign tumors in the thyroid of rats, called follicular adenomas, and hibernomas. Follicular adenomas are benign lesions consisting of a type of cells in the thyroid gland called follicular cells. In humans, hibernomas are rare, benign tumors consisting of brown fat tissue. The relevance of these animal findings to humans is unclear. Among participants who received itacitinib in clinical trials, there was no case of thyroid tumor reported thus far.

Treatment Group C (itacitinib 300 mg BID in combination with corticosteroids) was discontinued in this study after review of preliminary data due to a potential safety issue of increased malignancy relapse. Although no interim analysis was planned and the number of participants is small, with 4 confirmed relapses reported in this cohort versus 1 relapse in each of the 300 mg QD and 400 mg QD cohorts and no relapse in the corticosteroids alone cohort), the sponsor had decided to discontinue the itacitinib 300 mg BID study arm.

There may be unforeseen and potentially serious risks with itacitinib. More detailed information about the known and expected benefits and risks and reasonably expected AEs of itacitinib may be found in the IB.

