10.4.2.2. Part 1 Expansion

For Part 1 Expansion, the key secondary endpoints are response rate at Month 3 and Month 6, which are defined as the proportion of participants who demonstrate a CR or PR at each timepoint. The analysis will be conducted once the last participant completes Month 3 and Month 6 visits or withdraws from the study by treatment group for response rates at Month 3 and

Month 6, respectively. Summary statistics and 95% CI will be provided by cohort. The primary comparisons in Part 1 expansion will involve only the 2 itacitinib groups (A and B) and the corticosteroid alone group (D) as a result of Protocol Amendment 8, which discontinued Group C (300 mg BID + corticosteroid). Group C data will be presented only as summary statistics but will not be subjected to any statistical comparison.

Pairwise CMH tests will be conducted to Month 6 response rate for each of the 2 itacitinib groups (Treatment Group A and B) and the corticosteroids-only group (Treatment Group D) as an exploratory analysis.

The following secondary endpoints will be summarized by Treatment Groups A, B, and D using the ITT population for efficacy-related endpoints and all groups for safety-related endpoints:

- Response rate at 12 months, defined as the proportion of participants who achieved response (CR or PR) at Month 12.
- Time to response, defined as the interval between randomization and first response.
- DoR, defined as the interval between first response and cGVHD progression, death, or initiation of new systemic cGVHD therapy.
- OS, defined as the interval between the date of randomization and the date of death due to any cause.
- NRM, defined as the proportion of participants who died due to causes other than a relapse of their primary hematologic disease.
- Proportion of participants with ≥ 50% reduction in daily corticosteroid dose at Day 180.
- Proportion of participants successfully tapered off all corticosteroids at Day 180.
- Relapse rate of malignant and nonmalignant hematologic diseases, defined as the proportion of participants whose underlying disease relapses.
- Time to primary hematologic disease relapse, defined as the interval between the date of randomization and the date of relapse. Data from clinical safety assessments (eg, AEs, infections) will be listed and tabulated by treatment group.

10.4.2.3. Part 2

The following secondary endpoints will be summarized by treatment group using the ITT population:

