7.3.7. Relapse Rate of Malignant and Nonmalignant Hematologic Diseases

Relapse rate of malignant and nonmalignant hematologic diseases is defined as the proportion of participants whose underlying disease relapses. Relapse rate of malignant and nonmalignant hematologic diseases will be provided with a 95% CI. The CI will be calculated based on the exact method for binomial distributions. Cumulative incidence rate and summary statistics will be provided.

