9.2.4. Clinically Notable Adverse Events Based on Customized MedDRA Queries

There are 9 categories of clinically notable TEAEs (ie, categories of erythropenia [anemia], neutropenia, thrombocytopenia, CMV infections, EBV infections, hyperlipidemia, QT prolongation, thromboembolic events, fungal infections) that, in particular, are of scientific and medical interest specific to itacitinib and the GVHD population. The lists of MQs are in [Appendix B](#) through [Appendix F](#).

Within each category, the number and percentage of participants with at least 1 event occurring during treatment tabulated by MedDRA PT will be summarized. Summaries of clinically notable AEs based on customized MQs will be provided by category, PT, and the maximum severity.

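### On the plan's own labels the relapse tables omit Group C, the arm closed over relapse, and no text ensures that it is shown

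*SAP*

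**What the plan says.** Protocol 2.4 (Benefit/Risk Assessment) says Group C was discontinued "due to a potential safety issue of increased malignancy relapse". Protocol 2.3.2.3 gives the counts behind that decision: "with 4 confirmed relapses reported in this cohort versus 1 relapse in each of the 300 mg QD and 400 mg QD cohorts". For Group D it reports none.

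The endpoint tables place relapse elsewhere. Protocol Table 6 and SAP Table 1 list relapse rate and time to relapse under the objective of estimating efficacy outcomes. In the SAP the two endpoints are Sections 7.3.7 and 7.3.8, within the part on secondary efficacy parameters. SAP 7.3.7 reads: "Relapse rate of malignant and nonmalignant hematologic diseases is defined as the proportion of participants whose underlying disease relapses". Their outputs, Tables 2.2.5 and 2.2.6 in SAP Appendix A, are in the same series as response and survival.

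The rule on which groups are shown closes SAP 7.3.1: "The secondary endpoints discussed below will be summarized by Treatment Groups A, B, and D using the ITT population for efficacy-related endpoints". Protocol 10.4.2.2 has the same rule: "The following secondary endpoints will be summarized by Treatment Groups A, B, and D using the ITT population for efficacy-related endpoints". Each sentence then says that all groups are used where an endpoint is safety-related.

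**The concern.** The same outcome is a safety matter when the arm is closed and an efficacy outcome when the tables are specified. The display rule turns on that label. A programmer who follows the headings would build the two relapse tables with columns for A, B and D only.

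Relapse is the one outcome on which the study has closed an arm. The expansion exists to select a dose, and Protocol 6.1.1.4 says descriptive summaries of the other secondary endpoints feed into that choice. If Group C has no column, the planned relapse tables lack the 300 mg BID regimen. A reader of the study report could then not use them to compare relapse across the regimens studied, or to check the closure against final data.

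**Working it through.** **1. Counts (Protocol 2.3.2.3, cut-off 09 JUL 2021).** The text says "107 participants had been enrolled in the Part 1 expansion portion of the study". Enrolled by group: A 32, B 25, C 24, D 26. Sum: 32 + 25 + 24 + 26 = 107, which reproduces the stated total. Relapses: A 1, B 1, C 4, D 0; sum 6. Group C's share is 4/6 = 66.7%.

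**2. Rate by group.** SAP 7.3.7 specifies an exact binomial interval. For x events in n participants the 95% limits are the 2.5% quantile of Beta(x, n − x + 1) and the 97.5% quantile of Beta(x + 1, n − x). The lower limit is 0 when x = 0.

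| Group | x/n | Rate | Exact 95% CI |
|---|---|---|---|
| A (300 mg QD) | 1/32 | 3.1% | 0.1% to 16.2% |
| B (400 mg QD) | 1/25 | 4.0% | 0.1% to 20.4% |
| C (300 mg BID) | 4/24 | 16.7% | 4.7% to 37.4% |
| D (corticosteroids) | 0/26 | 0% | 0% to 13.2% |

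The A/B/D rule removes the third row. The remaining rows hold 2 of the 6 events, and none has a rate above 4.0%.

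**3. Sensitivity to the denominator.** Final counts are not in the documents. If every group filled to the planned 35 with no further relapse (an assumption), C would be 4/35 = 11.4% (3.2% to 26.7%), A and B 1/35 = 2.9% each, and D 0/35. Group C would still hold 4 of 6 events.

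**4. Does the safety clause bring Group C back?** Not reliably.
- In Protocol 10.4.2.2 the list under the rule ends with a line on tabulating clinical safety data such as adverse events and infections. That line gives the clause a natural object other than relapse.
- In the SAP the rule governs Sections 7.3.2 to 7.3.9, all under an efficacy heading, and none is marked as safety-related.
- Appendix A does not list the columns of Tables 2.2.5 and 2.2.6.

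**5. Do other outputs replace the missing column?** Only in part.
- SAP 9.2.4 says "There are 9 categories of clinically notable TEAEs"; none of them is relapse.
- SAP 9.2.1 ends the treatment-emergent window 30 days after the last dose, so later relapses fall outside it.
- Protocol 9.1 keeps efficacy endpoints out of adverse event reporting and then narrows this to progression of the disease under study. Because relapse is listed among efficacy outcomes, its capture as an adverse event is unclear.
- SAP 6.2 summarizes disposition with the primary reason for stopping treatment. That shows relapses recorded as the primary reason, with no relapse rate over all randomized participants, no interval and no cumulative incidence.
- SAP 9.1 has a rule for the Group C switch to 400 mg QD in the adverse event tables. SAP 7.3.7 and 7.3.8 have none for relapse.

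**The case against.** The strongest reply is that the plan is ambiguous and does not order the omission. The rule's second half keeps all groups for safety-related endpoints, and within SAP 7.3.2 to 7.3.9 it has little to act on unless something like relapse counts as safety. An outcome that closed an arm on safety grounds is the obvious candidate. SAP 7.3.1 also says Group C data will be presented as summary statistics, and the objective that covers relapse refers to each treatment cohort.

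Part of this stands. A reader might infer that Group C is certain to be dropped, and the documents do not go that far. They do not secure its inclusion either: the summary-statistics sentence belongs to the response-rate text, and the objective is a general statement, not a table rule.

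A reader might also infer that the signal vanishes from the report. It does not. Protocol 7.1.1 requires withdrawal from study treatment on relapse, and Protocol 2.3.2.3 already reports malignancy relapse as Group C's most frequent reason for discontinuation, so the disposition table should show it. SAP 9.1 also promises an overall adverse event summary spanning the period before and after the dose switch.

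Nor do the documents show that the dose decision would be made blind to relapse. SAP 9.3 gives the DMC a full review of safety, efficacy, tolerability and PK data, and it was the DMC that recommended closing the arm. Its charter is not among the documents.

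**Conclusion.** The point holds as a defect in a stated display rule. By the plan's own labels, the arm with 4 of the 6 reported relapses gets no relapse rate, interval or cumulative incidence, and no sentence ensures otherwise.

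The size rests on crude counts from an ad hoc cut. Follow-up was uneven: exposure in the itacitinib groups ran from 2 to 579 days. The figures show what the tables would lose; they do not estimate a dose effect.

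Pooling gives 6/107 = 5.6% with Group C and 2/83 = 2.4% without it. A reader might take this as the distortion in a planned result, but the plan reports relapse by group and no pooled rate is planned.

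The evidence concerns relapse. The documents report no signal for overall survival or nonrelapse mortality in Group C, so they do not support an equal claim for those endpoints.

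**What to change.** In SAP 7.3.1, state that relapse rate and time to primary hematologic disease relapse are treated as safety-related for the group rule. Summarize them descriptively for all four groups as randomized, with no statistical comparison involving Group C. In SAP 7.3.7 and 7.3.8, flag each Group C relapse as before or after the switch to 400 mg QD, in line with the adverse event handling in SAP 9.1.

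Nonrelapse mortality may be shown the same way because relapse is its competing event (SAP 7.3.6). Adding overall survival is optional. Protocol 10.4.2.2 can be aligned at the next amendment; the SAP change need not wait for it.

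The cost is a short SAP text change and one more column in Tables 2.2.5 and 2.2.6, plus Table 2.2.2 if nonrelapse mortality is included. No new data are needed. The downside is a sparse column with truncated 300 mg BID exposure, which must be labelled as such.
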